1.4.1.3 Outcomes

Primary Outcomes: For both sleep tests, the following are the primary outcomes for each participant:

- % of time spent in the supine and right-lateral positions with each intervention
- PrenaBelt User Feedback Questionnaires

The following data will be collected from each participant across each intervention and serve as pilot data to inform effect size calculations for future research.

- Apnea Hypopnea Index (AHI)
- Arterial blood oxygenation (SpO_2)
- Maternal heart rate (ECG)
- Sleep parameters (total sleep time, presence of snoring, RDI, sleep onset latency, sleep efficiency, sleep quality, number of arousals, number of position changes, mean AHI while supine, mean SpO_2 while supine)

When the two sleep tests are complete (interpreted and reported by the sleep specialist physician), the results will be provided to the participant's maternity care physician who will discuss her results with her at her next antenatal care visit. If warranted by the results of the sleep tests for a given participant (e.g., severe obstructive sleep apnea is discovered), contact will be made with the participant and her maternity care physician by a researcher to allow for proper management and care at the earliest opportunity. If her maternity care physician has any concerns about the sleep test results and plan for further investigation/management, he/she may consult with [name] (Site-Investigator, Respirologist, Sleep Specialist Physician) who will be available to address these concerns.

1.4.1.4 Inclusion/Exclusion Criteria

Inclusion criteria: ≥ 18 years old, low-risk singleton pregnancy, in the last trimester of pregnancy (≥ 28 weeks of gestation), and residing in the Halifax Regional Municipality.

Exclusion criteria: $\text{BMI} \geq 35$ at booking (first antenatal appointment for current pregnancy), pregnancy complicated by obstetric complications (hypertension [pre-eclampsia, gestational hypertension, chronic hypertension], diabetes [gestational or not], or intra-uterine growth restriction [$< 10^{\text{th}} \text{ %ile}$ for growth]), sleep complicated by medical conditions (known obstructive sleep apnea, known to get < 4 hours of sleep per night due to insomnia, or musculoskeletal disorder that prevents sleeping on a certain side [e.g., arthritic shoulder]), multiple pregnancy, known fetal abnormality, non-English speaking and reading.

1.4.1.6 Justification of Statistical Methods

Cross-over study design: each participant is her own control for comparison.

Descriptive statistics (mean, median, standard deviation, maximum, minimum) for demographic and sleep habits information and sleep variables (Section **Error! Reference source not found.**) will be reported.

For continuous variables, the assumption of normality will be assessed using Q-Q plots and the Anderson-Darling test. If normal, paired t-test will be used for evaluating differences. If non-normal, Wilcoxon signed rank test will be used for evaluating differences. For dichotomous data, we will evaluate for differences using McNemar's test for repeated measurements.

1.5 Timeline

November 2014 to May 2015: Halifax study preparation, PrenaBelt development and production of test samples, obtain ethical and research protocol approval from the IWK Health Centre REB.

November 2015 to July 2016: Training, recruitment, consent, enrolment, and data collection in Halifax.

July 2016 to August 2016: Data analysis, report writing, dissemination of findings from Halifax.

November 2014 to May 2015: Ghana study preparation, obtain ethical and research protocol approval from Noguchi Memorial Institute for Medical Research IRB, IWK Health Centre REB, and the Ghana FDA.

April 2015 to July 2015: Production of PrenaBelt test samples for Ghana study.

July 2015 to January 2016: Training, recruitment, consent, enrolment, and data collection in Ghana.

January 2016 to May 2016: Data analysis, report writing, dissemination of findings from Ghana.

1.6 Definition of Adverse Events

Labour is a natural process, so it will be classified as an unexpected event (not an adverse event) in this study should it begin to occur during a sleep test.

³ Note: the EAS Form submitted to the IWK states that a maximum number of thirty (n=30) participants will be recruited. The discrepancy of five (n=5) participants is a buffer to account for an approximate drop-out rate of 20%.

Participants may experience minor irritation of skin in areas in contact with the stickers that hold the sleep electrodes on their body.

The sleep tests for a given participant may reveal that an adverse event has been occurring in her pregnancy without prior knowledge. The sleep test may reveal the presence of maternal obstructive sleep apnea (OSA). We do anticipate that OSA will be discovered in some participants – especially since OSA is common yet often undiagnosed in pregnant women [39] [40] [41] [38] [42] [43] [44]. This adverse event is not related to this study, rather it is related to other obstetric and medical factors and only discovered by this study. It should also be noted that any events (e.g., OSA) that we do observe would be already occurring without anyone's knowledge. If severe OSA is discovered during any of the sleep tests, we will notify the participant and her maternity care physician, give them the test results, and ask them to speak with one another at earliest opportunity to ensure proper management and care. Her maternity care physician will also be informed that if he/she has any concerns about the sleep test results and plan for further investigation/management, he/she may consult with [name] (Site-Investigator, Respirologist, Sleep Specialist Physician) who will be available to address these concerns.

Should a medical emergency occur, the sleep technologists at the Capital Health Sleep Disorders Clinic have been trained according to internal policies and procedures for handling emergencies and unexpected events during sleep tests. The sleep technologists will call EMS and provide basic life support (if needed) until EMS arrives. The sleep technologists are trained in CPR.

Although the risk is low, a participant may go into labour during the sleep study; therefore, our exclusion criteria excludes women at risk of pre-term labour, and we will not book any participants for a sleep test beyond 37 weeks gestation unless the participant is comfortable in doing so. The research assistant will follow a basic plan of action should the participant go into labour during a sleep test:

1. If a participant begins labour during a sleep test, stop the test immediately.
2. Urgent: if onset of labour is sudden and participant is in distress, call EHS to transport the participant to the IWK. Otherwise proceed to 3.
3. Non-urgent: if onset of labour is slow and participant is stable, use the information from the Unexpected Events Contact Form and assist the participant in reaching her contact to transport her to the IWK.

Pregnancy is associated with many risks for the mother and fetus, yet sleep tests are non-invasive and safe for pregnant women and their developing baby to undergo. Although the risks that this study poses to the pregnancy are minimal, all adverse events will be reported to the CDHA Patient Safety Reporting System as per hospital standard operating procedures.

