1.1.4 Hypotheses

The following are hypotheses for the study proposed for Halifax:

1. When compared to one night of sleep with no positional therapy (PT) treatment, treatment with a PT intervention (PrenaBelt) during one night of sleep in the third trimester of pregnancy will significantly reduce the percentage of time spent in the supine and right-lateral positions and, thereby, have a favourable effect on maternal respiratory and cardiovascular parameters.
2. Maternal satisfaction, comfort, and desire to continue use of the PrenaBelt during third trimester sleep will be acceptable¹ after one night of use.

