1.4.1.1 Methods

After the recruitment, consent, and enrolment processes (see Section 2.5), each participant will be contacted by a researcher and booked for two overnight sleep tests at the Capital Health Sleep Disorders Clinic (4th floor, Abbie J Lane Building, QEII Hospital, [name]). These sleep tests will be booked to take place late in her pregnancy (28-37 weeks) but not beyond 37 weeks unless she is comfortable doing so. These two tests need not be consecutive nights as this may be onerous on the participants, who may have children at home; we will accommodate the schedules and wishes of the participants. The sleep clinic has two beds that can be dedicated to research; therefore, two participants should be booked into the clinic per night for budgetary reasons: two participants can be monitored by one research assistant in a twelve hour shift (see section 1.7).

Each participant will be told that she will be randomized by the researchers to which intervention – PrenaBelt device or sham-PrenaBelt – she will receive on the first night and not informed of the treatment order. On the second night, each participant will be switched over to the alternate intervention. Since the PrenaBelt and sham-PrenaBelt will be virtually identical (except for functional PT capability), each participant will be essentially blinded to the intervention received on each night. The PrenaBelt and sham-PrenaBelt will be randomly labeled as either “Device A” or “Device B” by one of the researchers not directly involved in sleep test monitoring, scoring, interpretation, or reporting. The research assistant monitoring and sleep technologist scoring the sleep tests and the sleep specialist physician interpreting and reporting the results will be blind to the intervention used on each night because they will not be told the true identification of “Device A” and “Device B”. As such, this triple-blind, cross-over, sham-controlled design enables each participant to serve as her own control and measurements/results can be compared between her sleep tests.

In preparing for the sleep tests, each participant will be directed to follow the instructions within the Information and Consent Form, which are standard instructions that the sleep clinic has published on its website:

- Participants will be asked to not drink alcohol on the days of their sleep tests.

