2.4 Minimization of Potential Harms

While the risks of this study to the participants and their developing babies are minimal, all adverse events will be reported to the CDHA Patient safety Reporting System as per hospital standard operating procedures

Wearing the PrenaBelt and sleep monitoring equipment may be uncomfortable for a participant and disturb her sleep. Each participant will be instructed how to, and told that she can, remove these devices and discontinue use at any time if she becomes too uncomfortable. If bothersome skin irritation occurs for a given participant as a result of contact with the electrodes, we will limit the contact of sleep electrodes to one overnight study.

Personal health information (PHI) used to identify potential participants will not be accessed by anyone other than the researchers within their circle of care.

Upon enrolment in the study, each participant will be assigned a random, six-digit, alphanumeric code. All data collected from participants during the studies will be collected only in association with this code, thus automatically de-identifying the data and minimizing the risk of identification. The key to the code, which links the codes to patient names and contact information, will be kept in a secure location away from the de-identified study data, thus minimizing the risk of re-identification. The de-identified data in forms (paper) and files (electronic) will be secured in a locked filing cabinet and in password-protected files on a password-protected computer, respectively, in a locked office with limited access.

For all study activities, all data collected from participants will be protected from unauthorized access to safeguard participant privacy and confidentiality in accordance with TCPS2, PHIPA, and PIPEDA and personal information policies at the IWK Health Centre.

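### Section 1.6 takes all labour during a sleep test, pre-term labour included, out of the adverse-event definition on which the protocol's only stated safety-reporting route depends

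*Protocol*

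**What the plan says.** **Classification.** Protocol section 1.6 states: "Labour is a natural process, so it will be classified as an unexpected event (not an adverse event) in this study". The reason given is that labour is natural, and gestational age does not enter the rule.

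**Timing.** Section 1.4.1.1 gives the window: "These sleep tests will be booked to take place late in her pregnancy (28-37 weeks"; later tests are allowed if the woman is comfortable with that.

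**Risk acknowledged.** Section 1.6 also says: "Although the risk is low, a participant may go into labour during the sleep study". It then claims that the exclusion criteria keep out women liable to pre-term labour, and sets out an action plan that begins: "If a participant begins labour during a sleep test, stop the test immediately". The remaining steps concern transport.

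**Reporting.** Section 1.6 commits that "all adverse events will be reported to the CDHA Patient Safety Reporting System as per hospital standard operating procedures". Section 2.4 repeats the commitment with the same trigger: "all adverse events will be reported to the CDHA Patient safety Reporting System".

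**Sleep apnoea found by a test.** Section 1.6 says of obstructive sleep apnoea (OSA): "This adverse event is not related to this study, rather it is related to other obstetric and medical factors and only discovered by this study".

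**SAP.** Section 2 lists no safety outcome, section 5 plans no interim safety analysis, and section 6 describes no safety listing.

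**The concern.** Reporting is triggered by a term, and labour has been defined out of that term. At term, calling labour a natural process is understandable. Before term, labour is a complication that the protocol itself says it wants to avoid, yet the exemption applies equally from 28 weeks.

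The device is described as a prototype that creates pressure points around the midriff, and the protocol says positional therapy has not been studied in pregnancy (section 1.1.3). Whether a particular labour onset had anything to do with the device or the test night is therefore a question to assess for each event. A definition written beforehand should not settle it. What is at stake is the completeness of the safety record of a first study in this population. The position and sleep analyses are not affected.

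**Working it through.** The plan gives no figure on this point, so the check is mainly textual.

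**Step 1. Can labour during a test be pre-term?** Yes. Tests run from 28 weeks (section 1.4.1.1). The documents do not define pre-term; I assume before 37 weeks. Tests beyond 37 weeks are possible, so not every labour onset would be early. The documents do not say how many nights fall on each side.

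**Step 2. Does the stated reporting route reach it?** No. Sections 1.6 and 2.4 report adverse events; section 1.6 says labour is not one. Neither document has a sentence that reports unexpected events.

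**Step 3. Does anything else in the documents capture it?**

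| Candidate | What it does |
|---|---|
| Labour action plan (1.6) | Stops the test and arranges transport; no recording or reporting step |
| Clinic policies (1.6) | Said to cover the handling of emergencies and unexpected events; reporting not mentioned |
| Unexpected Events Contact Form (2.4) | Holds contact details only; shredded after the second test |
| Data Collection Form (1.4.1.1, 1.4.1.2) | Asks about new pregnancy conditions, but is completed on the first test night only, at arrival or around hook-up |
| User Feedback Questionnaire (1.4.1.2) | Position, satisfaction, comfort, intention to use, suggestions |
| SAP sections 2, 5, 6 | No safety outcome, interim safety analysis or listing |

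None of these creates a reported or listed event.

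**Step 4. Is the stated safeguard in place?** Section 1.6 says women at risk of pre-term labour are excluded. Section 1.4.1.4 lists hypertension, diabetes, growth restriction, multiple pregnancy and fetal abnormality, together with BMI, sleep and language criteria. Risk of pre-term labour is not among them; the nearest wording is the general requirement of a low-risk singleton pregnancy. The two sections do not agree.

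**Step 5. The OSA statement.** Section 1.1.4 hypothesises that the belt will "have a favourable effect on maternal respiratory and cardiovascular parameters", so declaring a respiratory finding unrelated in advance sits awkwardly with the trial's aim. But the sentence itself calls OSA an adverse event, so it stays within the reporting commitment. AHI and SpO2 are measured on both nights (Protocol 1.4.1.2 and 1.4.1.3; SAP section 2) and compared by paired tests (SAP section 6). This is a fault in how relatedness is judged; reporting of OSA is not lost.

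**Step 6. Scale, for context only.**
- Exposure: 30 women × 2 nights = 60 nights at most, 30 with each device.
- No labour rate is given. Assuming independent nights and an illustrative chance p of onset per test night, the chance of at least one event is 1 − (1 − p)^60: 5.8% for p = 0.1%, 26.0% for p = 0.5%, 45.3% for p = 1%.
- With no events, the one-sided 95% upper bound per woman is 1 − 0.05^(1/n): 9.5% for n = 30 and 11.3% for n = 25. The plan makes no such calculation. The bound only shows that a zero count from so small a study says little, so a single event would be worth having on record.

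**The case against.** The strongest reply is that this is a gap in wording in a low-risk study. The protocol calls the risk of labour low. Labour has its own category and action plan. A stopped test would show as an incomplete night. Reporting follows hospital procedures that are not in the documents and may well cover labour. Most of this is fair, and it limits the severity. It does not remove the point: an incomplete recording carries neither gestational age nor a relatedness judgement into any listing, and the protocol does not say that the hospital procedures override its own definition.

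The reply is fully right against several stronger readings that a reader might infer:

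- **That no obstetric adverse event could be reported.** Only labour is exempted by name.
- **That no device-related respiratory event could be reported.** OSA is still called an adverse event, and severe OSA is also notified to the participant and her physician. The remark about events already occurring comes in a paragraph about conditions that a sleep test uncovers; in context it is not a causality rule for the whole trial.
- **That later trials would lean on a falsely clean safety record.** Sections 1.1 and 1.4.1.5 speak only of effect-size calculations.
- **That the belt might provoke labour.** The documents give no mechanism, and section 2.2 reports pelvic belts used in sleep without reports of serious adverse effects.

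**Conclusion.** The point holds for labour, and most clearly for pre-term labour. Section 1.6 exempts it whatever the gestation, the only stated reporting route depends on the exempted term, and nothing else in either document records or lists it. This is a wrong rule rather than a missing detail, because following it as written leaves the event unreported.

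The size is modest: at most 60 test nights, a risk that the protocol calls low, and no effect on the primary outcomes. It should be corrected, but it does not threaten the trial. The advance statement about OSA is a secondary matter of wording.

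The conclusion assumes that pre-term means before 37 weeks and that the unseen hospital procedures do not already require labour to be reported. If they do, the protocol's wording still conflicts with them and needs correction.

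**What to change.** 1. In section 1.6, remove the blanket exemption of labour from the adverse-event definition, at least for labour before 37 weeks.
2. Record any labour onset during a test with gestational age, clock time and device code (A or B), and report it through the Patient Safety Reporting System route already named in sections 1.6 and 2.4.
3. Have relatedness assessed case by case while blinded, and add to SAP section 6 a listing of these events by device night.
4. Reconcile the section 1.6 statement about excluding women at risk of pre-term labour with the criteria in section 1.4.1.4. Which text should change is for the sponsor to decide.
5. Secondary: replace the advance statement that discovered OSA is unrelated with the same case-by-case assessment. The AHI and SpO2 comparisons do not change.

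The labour action plan stays as it is. The cost is a few sentences, one short event form and one listing. The small downside is that some events unrelated to the belt will appear in the listing.

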- f. Sleep staging: via electroencephalography (EEG), electromyography (EMG), and electrooculography (EOG). Note that if a participant is uncomfortable or cannot tolerate some of the EEG, EMG, or EOG electrodes/leads, e.g., EMG electrodes/leads on arms and legs, these electrodes/leads may be removed.

In the morning following each sleep test, before each participant is discharged home, she will be asked to complete the approved PrenaBelt User Feedback Questionnaire and seal it in a provided envelope for the researchers. Participants will be asked:

- a. What position she adopted upon settling down last night
- b. What position she fell asleep in last night
- c. What position she woke up in this morning
- d. If she changed position during night
- e. If she remembers changing positions
- f. Her level of satisfaction with the PrenaBelt as it relates to the quantity and quality of her sleep last night
- g. Her level of comfort while wearing and sleeping with the PrenaBelt
- h. Her intention to use the PrenaBelt for the remainder of her pregnancy if it was available to her
- i. Any suggestions of changes/ modifications/ improvements she may have for the PrenaBelt

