2.2 Potential Harms to Participants and Others

This study is minimal risk. Participants in this study are at no greater risk of harms when completing the activities of this study than those risks they encounter in their everyday life.

The PrenaBelt device is a non-invasive medical device of Class I designation (see section 1.1.3). Pregnant women typically sleep with many pillows supporting their body, including a pillow behind their back to avoid the supine position. The PrenaBelt is a positional therapy device that may assist pregnant women to avoid supine sleep. Positional therapy devices have been shown to be safe and approved for use by humans by the US Food and Drug Administration [37]. In addition, maternal body pillows, regular pillows, and pelvic belts (lumbar support) have been used by pregnant women during sleep without reports of serious adverse effects for the mother or neonate [51].

In Halifax, wearing the PrenaBelt and sleep monitoring equipment may be uncomfortable for a participant and disturb her sleep. Each participant will be told that she can remove these devices at any time overnight if she becomes too uncomfortable.

In order to ensure the monitor electrodes remain adhered to participant's skin, the research assistant will need to prepare the area of skin, which involves cleaning and slight abrasion with an abrasive skin preparation gel. In the morning, after the monitors are removed, participants may experience slight discomfort and redness on the regions of their skin that were in contact with the electrodes. Rarely, a person will have a minor skin reaction on the area of his/her skin that was in contact with the electrodes. This reaction is not dangerous and usually goes away on its own within 24 hours to a few days.

Since personal information will be collected from participants, there always exists the potential harm should breach of confidentiality inadvertently occur.

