### ***2. Outcome measurements***

Primary Outcomes:

- % of time spent in the supine and right-lateral positions with each intervention
- PrenaBelt User Feedback Questionnaires

Secondary outcomes:

- Apnea Hypopnea Index
- Peripheral blood oxygenation (SpO2)
- Maternal heart rate
- Sleep parameters (total sleep time, presence of snoring, RDI, sleep onset latency, sleep efficiency, sleep quality, number of arousals, number of position changes, mean AHI while supine, mean SpO2 while supine)

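### Belt-related adverse events beyond comfort, sleep and device removal are not named, not visibly asked about, and not planned for tabulation by device

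*Protocol*

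**What the plan says.** **What counts as an adverse event.** Protocol 1.6 deals with four things.
- Labour: "it will be classified as an unexpected event (not an adverse event) in this study should it begin to occur during a sleep test".
- Electrode contact: "Participants may experience minor irritation of skin in areas in contact with the stickers that hold the sleep electrodes on their body".
- Sleep apnoea found by the test: "This adverse event is not related to this study, rather it is related to other obstetric and medical factors".
- Medical emergencies.

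The reporting rule is general: "all adverse events will be reported to the CDHA Patient Safety Reporting System as per hospital standard operating procedures". It states no checklist, time window, or attribution to a night or device. The skin provision in Protocol 2.4 is also tied to the electrodes: "If bothersome skin irritation occurs for a given participant as a result of contact with the electrodes".

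**What is said about the belt.** Protocol 2.2 accepts that "wearing the PrenaBelt and sleep monitoring equipment may be uncomfortable for a participant and disturb her sleep". Protocol 1.4.1.1 has the research assistant log removal of either device for intolerance.

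**What the women are asked.** Protocol 1.4.1.2 lists nine questionnaire topics for the morning after each night. Five concern body position. The others are satisfaction with sleep, "Her level of comfort while wearing and sleeping with the PrenaBelt", intention to keep using the device, and suggestions for improvement. The questionnaire is a primary outcome in Protocol 1.4.1.3 and SAP 2.

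**What is analysed.** Under "Secondary outcomes", SAP 2 lists respiratory, oxygenation, heart-rate and sleep measures. Neither SAP 2 nor SAP 6 mentions adverse events or device removals, and SAP 5 plans no interim safety analysis.

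**The concern.** The protocol itself makes belt harm foreseeable. Section 1.1.3 explains that pressure on the back and right side prompts the woman to move to relieve discomfort, and that the belt may instead be worn higher, with its front at the level of the fundus. Section 2.3.1 describes the tennis-ball method as similar in mechanism, and Attachment 1 gives back discomfort as one of that method's drawbacks. Sections 1.1.3 and 2.3.1 state that positional therapy has not been studied in pregnant women.

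For a prototype in that position, a basic harm record is part of what a feasibility study should deliver. Objective 2 concerns feasibility and acceptability, and the results are meant to inform larger trials. As written, the study could report that the belt was acceptable and have no systematic count of pain, pressure marks, numbness or abdominal symptoms. The sham night could separate belt effects from those of electrodes and the laboratory, but it has no planned use for these events. If the question is not asked on the morning, the information cannot be recovered at analysis.

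**Working it through.** **1. The plan's own figure.** The only design figure is the sample size: 25 pairs, one-sided α = 0.05, power 0.80, d = 0.5 in absolute value. The normal approximation gives ((1.645 + 0.842)/0.5)² = 24.7, rounded up to 25, which matches. With the t distribution, power at 25 pairs is 0.783. The plan recruits 30 to allow for losses. None of this concerns safety, but it fixes the denominators at 25 to 30 PrenaBelt nights.

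**2. Which belt harms are captured?**

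| Possible belt harm | Named as a risk | Asked or recorded on both nights | Analysis in SAP |
|---|---|---|---|
| Discomfort | Protocol 2.2, 2.4 | Comfort rating | Questionnaire is a primary outcome |
| Disturbed sleep | Protocol 2.2, 2.4 | Satisfaction rating and sleep recording | Primary and secondary outcomes |
| Intolerance leading to removal | Protocol 1.4.1.1 | Logged by the research assistant | None named |
| Pain, skin marks or reaction under the belt, numbness, abdominal symptoms | No | Not among the listed topics | None |

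The last row is the gap. Uterine monitoring does not fill it: Protocol 1.4 mentions uterine parameters and contractions, but no uterine measure appears in the lists in 1.4.1.1 and 1.4.1.2 or in SAP 2.

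**3. Would the comfort rating stand in for it?** Acceptability is a rating of 5 or more on a 1-to-10 scale (footnote to hypothesis 2). A woman with marks or numbness who rates comfort at 5 counts as acceptable, and no event is recorded. The forms are sealed for the researchers, and Protocol 2.4 keeps them from the research assistant. No step carries a harm written there into event reporting.

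**4. What would asking give?** If all n women are asked and none reports a given event, the exact upper limits on its rate are:
- two-sided 95%: 1 − 0.025^(1/n), which is 13.7% for n = 25 and 11.6% for n = 30;
- one-sided 95%: 1 − 0.05^(1/n), which is 11.3% for n = 25 and 9.5% for n = 30.

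The documents give no harm rates, so the following rates are assumptions. The chance of at least one event in 25 women is 1 − (1 − p)^25: 39.7% at p = 2%, 72.3% at 5% and 92.8% at 10%.

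**5. Would a test be useful?** An exact two-sided McNemar test with all discordant women in one direction has p = 2 × 0.5^k. Five women give 0.0625 and six give 0.031, so at least six are needed. With 25 women and assumed belt-only and sham-only rates of 20% and 5%, power is about 17%; at 30% and 5% it is about 46%. Counts with intervals are the right output.

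**The case against.** A reader might infer that nobody is asked about belt harm and that the trial cannot compare harm between PrenaBelt and sham. The documents do not support this. Discomfort and disturbed sleep, the two belt harms that Protocol 2.2 names, are rated by every woman after both nights within a primary outcome. Removal of either device is logged and followed up. Total sleep time, sleep efficiency, arousals, oxygen saturation and heart rate are measured on both nights. All of these can be compared within woman.

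A reader might also infer that events are recorded only if a woman volunteers them, so that zero reports says nothing. That too goes beyond the documents. Women are watched by audio and video all night, the research assistant unhooks them in person, and the duty to report all adverse events is worded widely enough to include belt events. Zero removals on 25 PrenaBelt nights would bound the removal rate exactly as in step 4 of the working.

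Two further points stand. The questionnaire form and the hospital reporting procedures are not in the documents, so extra prompts cannot be excluded. The protocol also draws no safety conclusion: acceptability is defined by satisfaction, comfort and intention to use.

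What remains is narrower. Observation from another room does not reveal numbness or marks under a belt, and a general duty to report neither prompts the question nor produces a count by device. The small sample limits the harm record to description but does not make it worthless.

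**Conclusion.** The point holds as a gap in harm collection and reporting. Belt-related events other than discomfort, disturbed sleep and device removal are not named in Protocol 1.6, are not among the listed questionnaire topics, and have no planned table in the SAP. Neither the position estimate nor the acceptability ratings are affected.

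The gain from closing the gap is modest but real. Zero events among women who were all asked would support a two-sided exact 95% upper limit of 13.7% (n = 25) or 11.6% (n = 30). Under the current plan, zero reports would bound only events that were volunteered or seen. These limits assume that every woman answers after her PrenaBelt night. The conclusion also assumes that the approved questionnaire contains no harm item beyond the topics in Protocol 1.4.1.2; if it does, only the definition and the table are missing.

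**What to change.** 1. **Protocol 1.6:** name belt-related events, for example pain, pressure marks or skin reaction under the belt, numbness and abdominal symptoms.
2. **Questionnaire:** add one standard harm item, identically worded for both mornings. Keep it in the sealed form. The research assistant should not collect the answers, because that person is blinded, observes body position, and is separated from the questionnaires by Protocol 2.4; a report of pressure marks after night one could reveal the device before night two.
3. **Routing:** have the envelope opened promptly by study personnel who do not monitor, score or interpret the sleep tests, so that any event enters the existing reporting route.
4. **SAP 6:** add a descriptive within-woman table of adverse events and device removals (PrenaBelt night only, sham night only, both, neither), with rates by device night and exact 95% confidence intervals. Plan no hypothesis test. This also avoids relying on the binary-data test, where Protocol 1.4.1.6 names McNemar and SAP 6 names chi-squared or Fisher.

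The cost is about a minute per visit, one extra table, a minor amendment to the questionnaire, and staff time to open the envelopes promptly.
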